4.3.5 Subgroup analyses

To assess the homogeneity of the treatment effect across various subgroups, analyses will be performed on the primary endpoint (ISS7 and UAS7) across the following subgroups:

- Age group (<median, \geq median; <65 , ≥65 years)
- Gender (Male, Female)
- Baseline weight (<median, \geq median, <60 , ≥60 kg)
- Baseline BMI (<25 , ≥25 - <30 , ≥30 kg/m²)
- Region (see [Section 5.3](#))
- Territory (see [Section 5.3](#))
- Race (White, all the Others)
- Ethnicity (Hispanic, non-Hispanic)
- Angioedema at baseline (Yes, No)
- Baseline UAS7 score (<28 , ≥28)
- Baseline ISS7 score (<13 , ≥13)
- Duration of disease (<2 , 2-10, >10 years)
- H1-AH baseline dose (1-fold, 2-4-fold)
- Baseline Total serum IgE (<100 IU/mL, ≥100 IU/mL)

To assess the consistency of the treatment effects across the subgroup levels, subgroup analyses will be conducted for the primary endpoint at Week 24. The analysis will be performed based on imputed datasets from the primary analysis.

To test the interaction between intervention and subgroup factor, an ANCOVA model incorporating subgroup-by-treatment interaction will be built for each subgroup factor. The model will include all the covariates in the main statistical model plus the subgroup variable (if not one of the covariates adjusted in the main model already) and the subgroup-by-treatment interaction. Statistical inference obtained from all imputed data will be combined using Rubin's rule. A p-value for the test of interaction will be provided based on the combined inference.

In each subgroup, the primary endpoint will be analyzed using the primary approach for the primary endpoint, but on the specific subgroup of the imputed primary analysis population. Descriptive statistics including number of participants, mean, standard error, and least squares (LS) means for each subgroup will be provided. In addition, difference in LS means and the corresponding 95% confidence intervals (CI) will be provided for each subgroup. Forest plots will be provided.

In addition, the primary endpoint will be analyzed in the subgroups of adults and adolescent participants.

China subpopulation will be considered for primary efficacy, key secondary efficacy, and important safety analyses (which are for China submission and may be performed outside of the main Clinical Study Report).

4.4 SECONDARY ENDPOINT(S) ANALYSIS

4.4.1 Key/Confirmatory secondary endpoint(s)

4.4.1.1 *Definition of endpoint(s)*

Key secondary endpoints are indicated in [Table 1](#) and are presented below.

- Change from baseline in weekly urticaria activity score (UAS7) at Week 24 (primary for EU and EU reference countries).
- Change from baseline in ISS7 at Week 24 (in EU and EU reference countries).

The same intercurrent event handling strategy and missing data handling will be applied as the primary endpoint.

4.4.1.2 *Main analytical approach*

Continuous secondary endpoints will be analyzed using the same approach as the primary efficacy endpoint.

4.4.2 Supportive secondary endpoint(s)

The change from baseline in AAS7 at Week 12 and Week 24 will be analyzed in those participants who have angioedema at baseline defined as a baseline AAS7 score >0 . The change from baseline and percent change from baseline in continuous endpoints will be summarized and analyzed by week using the same approach as the primary endpoint. Descriptive statistics including number of participants, mean, standard error, and least squares (LS) means will be provided. In addition, difference in LS means and the corresponding 95% confidence intervals (CI) will be provided along with the p-values. Figures over time will also be presented.

The endpoint change from baseline in DLQI will be summarized and analyzed in participants ≥ 16 years old who completed the DLQI at baseline.

Responder endpoints will be analyzed using the CMH test adjusted by baseline disease severity, presence of angioedema at baseline, and region. The baseline disease severity will be defined according to UAS7 <28 or ≥ 28 . Comparisons of the response rates between dupilumab dose and placebo will be derived. Participants who receive selected prohibited medications and/or rescue medications will be considered as non-responders for time points after medication usage. For other participants, all available data including those collected during the off-treatment period will be used to determine the responder/non-responder status. Missing data will be considered as non-responders.

Time-to-event endpoints will be analyzed using the Cox proportional hazards model, including intervention, the corresponding baseline value, presence of angioedema at baseline, and region as covariates. The hazards ratio, its 95% confidence interval and p-value will be reported. Kaplan-Meier curves will be also provided.

For time to first ISS7 MID (ISS7 ≥ 5) response defined as time to reduction from baseline of 5 points or more, participants who receive selected prohibited medications and/or rescue

medications (see [Table 4](#)), data prior to start of the medication will be used, but after medication start, the participant will be censored at Week 24 (ie, Day 169). For other participants, all available data up to Week 24 (ie, Day 169) including those collected during the off-treatment period will be used. Participants without events will be censored at Day 169 or their last ISS7 assessment date if discontinued from the study whichever is earlier.

For time to participants receiving first OCS for CSU during the planned treatment period, participants who receive selected prohibited medications and/or rescue medications other than OCS for CSU, data prior to start of the medication will be used, but after medication start, the participant will be censored at time of start of medication. Participants who don't receive OCS during the treatment period will be censored at Day 169 or their status date collected on the completion of study/follow-up eCRF form, whichever is earlier. This endpoint will be analyzed using a Cox proportional hazards model, including intervention, presence of angioedema at baseline, and region as covariates.

Categorical summaries by visit will be provided for PGIC and PGIS.

In addition, secondary endpoints included in the multiplicity procedure ([Section 4.6](#)) will be analyzed in the subgroup of adults and adolescent participants.

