4.4 SECONDARY ENDPOINT(S) ANALYSIS

4.4.1 Supportive secondary endpoint(s)

The change from baseline in AAS7 at Week 12 and Week 24 will be analyzed in those participants who have angioedema at baseline defined as a baseline AAS7 score >0 . The change from baseline and percent change from baseline in continuous endpoints will be summarized and analyzed by week using the same approach as the primary endpoint. Descriptive statistics including number of participants, mean, standard error, and least squares (LS) means will be provided. In addition, difference in LS means and the corresponding 95% confidence intervals (CI) will be provided along with the p-values. Figures over time will also be presented.

The endpoint change from baseline in DLQI/CDLQI will be summarized and analyzed in participants ≥ 16 years old who completed the DLQI at baseline.

Proportion type efficacy endpoints will be analyzed similar to the key secondary endpoints above. The response rates at each week up to Week 24 will be summarized and plotted by intervention groups using the same method as other proportion type endpoints.

Time-to-event endpoints will be analyzed using the Cox proportional hazards model, including intervention, the corresponding baseline value, presence of angioedema at baseline, and region as covariates. The hazards ratio, its 95% confidence interval and p-value will be reported. Kaplan-Meier curves will be also provided.

For time to first ISS7 MID (ISS7 ≥ 5) response defined as time to reduction from baseline of 5 points or more, participants who receive selected prohibited medications and/or rescue

medications (see [Table 5](#)), data prior to start of the medication will be used, but after medication start, the participant will be censored at Week 24 (ie Day 169). For other participants, all available data up to Week 24 (ie, Day 169) including those collected during the off-treatment period will be used. Participants without events will be censored at Day 169 or their last ISS7 assessment date if discontinued from the study, whichever is earlier.

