| Secondary endpoint – Proportion | Proportion of ISS7 MID (≥ 5 points) responders at Week 12 and Week 24; Proportion of patients with UAS7 ≤ 6 at Week 12 and Week 24 Proportion of patients with UAS7 = 0 at Week 12 and Week 24 | ITT | 
The intercurrent events will be handled as follows:
 
 Discontinuation of study intervention (but not taking selected prohibited and/or rescue medications^b prior to Week 24): Off-study intervention data will be included in the analysis (treatment policy strategy). Taking selected prohibited medications and/or rescue medications^b before Week 24 (or Week 12): Participants will be considered as non-responders (composite strategy). 
After applying the rules for intercurrent events, if there is still missing data, then the missing data imputation rules are as follows:
 
 Having missing data at Week 24 (or Week 12): Participants will be considered as non-responders. | CMH test adjusted by presence of angioedema at baseline, region (combined countries), and baseline disease severity (UAS7 < 28 , ≥ 28) |
| Secondary endpoint – Time-to-event | Time to ISS7 MID response | ITT | 
The intercurrent events will be handled as follows:
 
 Discontinuation of study intervention before Week 24 (but not taking selected prohibited and/or rescue medications^b prior to Week 24): Off-study intervention data up to Week 24 will be included in the analysis (treatment policy strategy). Taking selected prohibited medications and/or rescue medications^b prior to Week 24: Analyses will be censored at Week 24 (composite strategy) 
After applying the rules for intercurrent events, if there is still missing data, then the missing data imputation rules are as follows:
 
 Discontinuing the study follow-up before Week 24: Analyses will be censored at the time of last ISS7 assessment. | This time-to-event endpoint will be analyzed using the Cox proportional hazards model, including intervention, the corresponding baseline value, presence of angioedema at baseline, and region. The hazards ratio, its 95% confidence interval and p-value will be reported. |

^a Additional secondary objectives/endpoints are not included in this table but would be handled with a similar strategy as the endpoint type (ie Continuous, proportion, time-to-event) at other weeks

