The primary efficacy endpoints will be analyzed using an analysis of covariance (ANCOVA) model with the baseline value of the primary endpoint, intervention group, presence of angioedema at baseline, and region as covariates, with intercurrent events and missing data being handled by a hybrid method of the worst-observation carried forward (WOCF) and multiple imputation. For participants taking selected prohibited medications and/or rescue medications (see [Table 4](#)), their data after the medication start date will be excluded, and the worst postbaseline value on or before the time of the medication usage will be assigned to the Week 24 value (for participants whose postbaseline values are all missing, the baseline will be used). Participants who discontinue the intervention prematurely are encouraged to follow the planned clinical visits and in these participants who did not take the selected prohibited medications and/or rescue medications, all data collected after intervention discontinuation will be used in the analysis. For these participants, missing data may still happen despite all efforts to collect the data after intervention discontinuation. For participants who discontinue study intervention due to lack of efficacy, all data collected after discontinuation will be used in the analysis, and a WOCF approach will be used to impute missing Week 24 value if needed (ie due to study discontinuation). For participants who discontinued study intervention for reasons other than lack of efficacy, a multiple imputation approach will be used to impute the missing Week 24 value. This multiple imputation will include all participants except participants who have taken the selected prohibited medications and/or rescue medications on or before Week 24 and will also exclude participants who discontinued study intervention due to lack of efficacy on or before Week 24.

Each of the imputed complete data will be analyzed by fitting an ANCOVA model as described above. Statistical inference obtained from all imputed data will be combined using Rubin's rule. Descriptive statistics including number of participants, mean, standard error, and least squares (LS) mean changes (and standard error) score will be provided. In addition, difference of the dupilumab group against placebo in LS means and the corresponding 95% confidence intervals (CI) will be provided along with the p-values.

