4.5.2 Main analytical approach

Exploratory efficacy endpoints will be analyzed using the same methodology as above for similar data (continuous, proportion, or time to event).

Time to first UAS7 change from baseline of ≥ 9.5 and ≥ 10.5 will be analyzed similar to time to ISS7 MID (ISS7 ≥ 5) response. For participants not receiving selected prohibited medications and/or rescue medications, all available data up to Week 24 (ie, Day 169) including those collected during the off-treatment period will be used. Participants without events will be censored at Day 169 or their last UAS7 assessment date on or before Day 169 if discontinued from the study, whichever is earlier.

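### Time to ISS7 and UAS7 MID response in Study C censors event-free study leavers at their last score even when they stopped for lack of efficacy, so the hazard ratio and Kaplan-Meier curves can be biased

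*SAP*

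**What the plan says.** In Study C SAP 4.4.2, the rule for time to ISS7 MID response is: "Participants without events will be censored at Day 169 or their last ISS7 assessment date if discontinued from the study whichever is earlier". The estimand table (1.2.1, Table 2) lists the same rule under missing data: "Discontinuing the study follow-up before Week 24: Analyses will be censored at the time of last ISS7 assessment". Section 4.5.2 applies it to time to UAS7 MID, where participants without events are "censored at Day 169 or their last UAS7 assessment date on or before Day 169 if discontinued from the study, whichever is earlier". None of the three places distinguishes reasons for leaving.

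The same SAP handles related participants as follows:

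- **Primary analysis (4.3.2), treatment stopped for lack of efficacy:** "a WOCF approach will be used to impute missing Week 24 value if needed (ie due to study discontinuation". These participants are also left out of the multiple imputation.
- **Responder endpoints (4.4.2):** "Missing data will be considered as non-responders".
- **Selected prohibited or rescue medication, same time-to-event endpoint (4.4.2):** "after medication start, the participant will be censored at Week 24 (ie, Day 169". Table 2 labels this a composite strategy.

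Stopping treatment does not by itself censor anyone, because off-treatment data up to Day 169 are used. The Study A SAP (4.4.1) has the same rule, "Participants without events will be censored at Day 169 or their last ISS7 assessment date if discontinued from the study, whichever is earlier", and so does the Study B SAP (4.4.2).

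**The concern.** The Cox model and the Kaplan-Meier estimator treat a censored participant as having the same future chance of response as comparable participants still under observation. That is doubtful for someone who never reached a 5-point reduction, stopped because the treatment was not working, and then left the study. If such people would mostly not have responded, censoring them removes non-responders from the risk set and raises the estimated response curve in the arm that loses them. The hazard ratio then depends on how many leave and from which arm.

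At stake are a hazard ratio, 95% confidence interval, p-value and Kaplan-Meier curves for a listed secondary endpoint, and the matching results for an exploratory one. The sensitivity and supplementary analyses in 4.3.3 and 4.3.4 concern the primary endpoint, so no planned analysis would show the effect of this rule.

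**Working it through.** **1. The rules side by side.** Take a participant with no weekly ISS7 reduction of 5 points or more, who stops treatment for lack of efficacy and leaves before Week 24 without selected rescue.

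| Analysis | Handling |
|---|---|
| Primary, Week 24 ISS7 | Worst post-baseline value (baseline if there is none) |
| ISS7 MID response at Week 24 | Non-responder |
| Time to ISS7 MID | Censored at last score |
| Time to ISS7 MID, had selected rescue been taken | Event-free to Day 169 |

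No post-baseline score of this person reached the MID, so the carried-forward value is itself an MID non-response. Only the third row leaves later response open.

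**2. The plan's own figure.** The documents give no hazard ratio, event count or power for this endpoint. The Study C figure available is the sample size (Protocol 9.2), and it reproduces. The effect size is 4.23/7.5 = 0.564. At 90% power and two-sided alpha 0.05, the normal approximation gives 67 per arm, and 67/0.90 = 74.4, rounded up to 75. With 75 × 0.90 = 67.5 evaluable per arm, the noncentral t power is 90.2%.

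**3. Size of the shift.** Assumed inputs:

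- *24-week response.* From the Study A mean changes (Protocol 2.1, Table 1) and SD 7.5, placebo is Φ((-5 + 6.01)/7.5) = 0.55 and dupilumab is Φ((-5 + 10.24)/7.5) = 0.76. A second pair, 70% and 85%, is a further assumption.
- *Leavers.* They depart at Weeks 4 to 19 and would never have responded. Their share per arm is varied.

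Hazard ratio for response, dupilumab against placebo (weekly Cox model, 400,000 per arm):

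| Leavers, placebo / dupilumab | 55% v 76%: held to Day 169 | 55% v 76%: as planned | Change | 70% v 85%: change |
|---|---|---|---|---|
| 3% / 1% | 1.760 | 1.742 | -1.1% | -1.2% |
| 5% / 2% | 1.760 | 1.736 | -1.4% | -1.6% |
| 8% / 2% | 1.755 | 1.691 | -3.6% | -4.1% |
| 10% / 3% | 1.773 | 1.703 | -4.0% | -4.7% |
| 15% / 3% | 1.770 | 1.630 | -7.9% | -9.6% |
| 2% / 2% | 1.761 | 1.774 | +0.7% | +1.1% |
| 5% / 5% | 1.762 | 1.800 | +2.2% | +2.9% |
| 2% / 6% | 1.760 | 1.859 | +5.6% | +7.3% |

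A second simulation, built from weekly score paths with SD 7.5, gave the same directions. At 10%/0% leavers the hazard ratio was 1.50-1.59 as planned against 1.60-1.73 with leavers kept at risk. At 5%/5% it was 1.57-1.61 against 1.49-1.52. At 10%/5% the log hazard ratio moved by 1-4%.

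**4. At 75 per arm (3,000 simulated trials).** With 55% v 76% response and 8%/2% leavers, the average hazard ratio is 1.71 as planned and 1.78 with leavers held to Day 169, and power is 76% and 81%. With equal true response (65% in both arms), the planned rule gives 0.95 for 8%/2% leavers, 1.05 for 2%/8% and 1.00 for 8%/8%. Rejection stays at about 4.5-5.5%.

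**5. Against sampling error.** Expected events are 75 × 0.55 + 75 × 0.76 ≈ 98, so the standard error of the log hazard ratio is about 2/√98 ≈ 0.20. The 10%/3% shift is ln(1.703/1.773) = -0.04, about a fifth of that. The 15%/3% shift is ln(1.630/1.770) = -0.08, about two fifths.

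**The case against.** The affected group is narrow. A participant must stop for lack of efficacy, leave the study as well, never have reached a 5-point reduction in any week, and not have taken a selected medication. The protocol works against this: those who stop are asked to complete remaining visits (7.1.1), and short-course OCS rescue, whose users are held to Day 169, is available (6.5.1). The 10% dropout is an all-cause allowance, so assigning most of it to this group is a stress case. This stands, and it limits the size.

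Holding leavers to Day 169 is also an assumption. Table 2 classes leaving follow-up as missing data, and the Study A mean placebo change of -6.01 lies beyond the 5-point threshold, so later response cannot be excluded. This stands too. The simulation makes leavers certain non-responders, so it overstates the shift if some would have responded. The Day 169 assumption is, however, the one the plan already makes for rescued participants here and in effect for these same leavers elsewhere.

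The endpoints are supportive or exploratory and are absent from the Study C hierarchy (4.6). Week 24 ISS7 MID response, with missing data as non-response, is tested there at rank 4.

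A reader might infer that only lack-of-efficacy leavers are removed from the risk set. They are not: every event-free study leaver is censored. Nor would a gap between the Kaplan-Meier curve and the Week 24 responder proportion prove this defect, because a participant can respond early and lose the response.

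**Conclusion.** The inconsistency is real and no planned analysis covers it. For lack-of-efficacy leavers, the time-to-response rule assumes a chance of later response that the primary, responder and rescue rules do not allow them. The hazard ratio and Kaplan-Meier curves can be biased as a result: toward 1 when clearly more placebo participants leave this way, away from 1 when leaving is equal under a real effect or higher on dupilumab.

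In the tabulated scenarios the hazard ratio changes by about -10% to +7%. When placebo leavers are 3-10% and exceed dupilumab leavers, the change is about -1% to -5%. These figures rest on assumed response rates, leaver shares and departure times, and on leavers never responding.

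Two stronger readings are tempting. One is that the hazard ratio is biased as a matter of fact, or biased in dupilumab's favour. The documents do not support it: they give neither the number nor the arm split of such leavers, and the shift is nil if nobody leaves this way. The other is that the trial's conclusion is at risk. It is not: both endpoints lie outside the hierarchy, and study success and alpha are unaffected.

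**What to change.** In Study C SAP 4.4.2, 4.5.2 and the time-to-event row of Table 2, add that participants who discontinue study intervention for lack of efficacy and leave the study without a prior response are censored at Day 169, as for selected prohibited or rescue medication. Keep last-assessment censoring for other study leavers. Report the present rule as a sensitivity analysis, which preserves comparability with Studies A and B. At minimum, keep the present rule as the main one and add the Day 169 rule as the sensitivity analysis. In either case, tabulate event-free study leavers by arm and reason.

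The cost is one SAP sentence, one extra model run per endpoint and a small table. The reason-for-discontinuation flag is already needed for the primary analysis. The protocol names the Cox model but sets no censoring rule (9.4.1, Table 7), so a SAP change before database lock is enough. The small downside is a departure from the main censoring rule of Studies A and B, which the sensitivity analysis covers.

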4.5 TERTIARY/EXPLORATORY ENDPOINT(S) ANALYSIS

4.5.1 Definition of endpoint(s)

Additional details are provided below for specific exploratory efficacy endpoints.

Time to UAS7 MID response (9.5 to 10.5 points) by Week 12 and Week 24

Time to first UAS7 reduction from baseline of 10.5 points or greater and 9.5 points or greater will be analyzed similar to time to ISS7 MID (ISS7 ≥ 5) response. Proportion of participants with each of these MID responses (10.5 and 9.5) by week will also be provided.

Change from baseline in the number of itch-free days and/or hive-free days at Week 12 and Week 24

Three endpoints will be summarized at each Week using descriptive statistics (mean, SD, min, max). Change from baseline in number of itch-free days, number of hive-free days, and number of itch and hive-free days over the 7 days.

Change in UAS7 in well-controlled patients (UAS ≤ 6) from Week 24 to 36. (only provide for final analysis)

For those participants who were well-controlled (UAS ≤ 6) at Week 24, the change in UAS7 from Week 24 to Week 36 will be summarized using descriptive statistics (mean, SD, min, max).

Use of antihistamine rescue medication

The number (%) of participants who received antihistamine as rescue medication during the planned treatment period (ie, up to Day 169) will be summarized by intervention group.

Total OCS rescue dose prescribed (in mg) during the treatment period

The total cumulative prescribed dose of OCS rescue medication will be summarized by descriptive statistics (mean, SD, min, max) over the planned treatment period.

Total OCS rescue intake in days during the treatment period

The total number of days that OCS rescue medication was taken during the planned treatment period will be summarized by intervention group.

EQ-5D-5L

The endpoint change from baseline in EQ-5D-5L index score (UK tariffs using the crosswalk method developed by Van Hout (2)) and EQ VAS will be summarized and analyzed in participants ≥ 16 years old who completed the EQ-5D-5L at baseline.

Proportion of participants with ISS7 = 0 and HSS7 = 0 at Week 12 and Week 24 will be summarized and analyzed similar to the secondary endpoint of UAS7 = 0. Cumulative number of itch and/or hive-free days from Week 4-12, 13-24, and Week 4-24 will be summarized and analyzed. This will be calculated as the number of days for which the participant indicated a 'No' response divided by the total number of days with a non-missing response during the period multiplied by the number of days in the period. Participants who withdrew before the Week 4 visit or who have missing responses for $>40\%$ of the daily entries during the period will not be included in the analysis.

The following additional exploratory analyses will be provided:

- Time to first select prohibited/rescue medication that impact efficacy (including medications where WOCF will be applied (see [Table 4](#))).
- A summary of the number (%) of participants with UAS7 categories (complete control (UAS7 = 0), well-controlled (UAS7 = 1 to 6), mild (UAS7 = 7 to 15), moderate (UAS7 = 16 to 27), and severe (UAS7 = 28 to 42)) at Week 24 by baseline UAS7 status (moderate or severe).

